6.5. Additional analyses: diagnostic test accuracy

6.5.1. Relationship between clinical examination signs and cardiac index

There is currently no consensus on how much cardiac index is sufficient for the critically ill patient. Different studies used differing cut-offs for a low cardiac index (15). Therefore, we will use 2 cut-offs for both a low and high cardiac index:

1. Cut-offs for a low cardiac index: 2.2 and 2.5 L/min/m²
2. Cut-offs for a high cardiac index: 4.0 and 4.5 L/min/m²

We will conduct a logistic regression with the dichotomised cardiac index and an ordinal logistic regression with a categorical cardiac index as the dependent variable. A univariable analysis will be conducted on all dependent (clinical examination) variables and a $p < 0.25$ will be used for inclusion in a multivariable model. Calibration of our multivariable model will be checked with a Hosmer-Lemeshow test and by plotting observed proportions of cardiac index against the predicted risks of 10 equally sized groups. We will identify the cardiac index cut-off(s) where clinical examination has the best discriminative value based on the area under the receiver operating characteristic (ROC)-curves.

Based on the multivariable logistic regression findings, we will construct a risk score for cardiac index based on the coefficients in the model. Scores will be calculated by dividing all coefficients by the lowest coefficient or by transforming all coefficients so that the score is easy to count.

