6.5.2. Diagnostic test evaluation

Depending on the optimal and number of cut-offs (i.e. low or normal cardiac index or low, normal and high cardiac index), we will display our diagnostic test in a 2 x 2 table, 2 x 3, or a 3 x 3 table (28,29). An example table can be found below. In a 3 x 3 table, data will be ordinal and we will give an indication of the agreement with the weighted kappa (30).

		Cardiac index cut-offs		
		Low (< 2.5)	Normal (2.5 to 4.5)	High (> 4.5)
EXAMPLE: Capillary refill time	Prolonged	True positive (a)	False positive (d)	False positive (d)
	Normal	False normal (b)	True normal (d)	False normal (b)
	Shortened	False negative (c)	False negative (c)	True negative (d)

Subsequently, we will calculate sensitivity, specificity, positive and negative predictive values and positive and negative likelihood ratios. Because this can only be calculated in 2 x 2 tables, we will cut the 3 x 3 table in low/normal and normal/high cut-offs:

		Cardiac index below/above x L/min/m ²	
		Yes	No
Clinical examination finding(s) present	Yes	True positive (a)	False positive (c)
	No	False negative (b)	True negative (d)

Explanation: x can be 2.2, 2.5, 4.0 or 4.5 L/min/m².

In addition, we will also calculate the 98.5% confidence intervals. Below we interpret each diagnostic test parameter for our diagnostic study.

- True positive: the number of patients with a low cardiac index who also had clinical examination signs indicating *hypoperfusion*.
- False positive: the number of patients without a low cardiac index, but with clinical examination signs indicating *hypoperfusion*.
- True negative: the number of patients without a low cardiac index and with clinical examination signs indicating *a normal* perfusion.
- False negative: the number of patients with a low cardiac index, but with clinical examination signs indicating *a normal* perfusion.
- Sensitivity: the probability of the presence of a low cardiac index when there were clinical examination signs indicating *hypoperfusion*.
- Specificity: the probability of the absence of a low cardiac index when clinical examination signs indicating *a normal* perfusion.
- Positive predictive value: the probability that a low cardiac index is present given the clinical examination signs indicate *hypoperfusion*.
- Negative predictive value: the probability that a low cardiac index is absent given the clinical examination signs indicate *a normal* perfusion.

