Our diagnostic hypotheses will be tested in two steps: first, we will investigate the association of cardiac index with clinical examination variables and second, we will investigate at which cardiac index the clinical examination findings of hypoperfusion become apparent. We aim to present a cut-off for low cardiac index relevant to critically ill patients in our secondary outcome, as current cut-offs for low cardiac index are based on patients with acute lung injury, heart failure or after cardiac surgery (16-20). Diagnostic test accuracies will be described for each finding or combinations of findings for our proposed cut-off of cardiac index. This secondary analysis, as well as the predefined subgroup analyses, will be considered exploratory and we will emphasise the need for validation in an independent cohort.

8. Conclusion

This SAP presents the principles of analysis of the SICS-I cohort and discusses its major methodologic and statistical concerns. We hope that the results of the SICS-I will be as transparent and robust as possible, so that we minimised the risk of outcome reporting bias and data-driven results.

9. Tables and figures

Figure 1. Flow diagram (example)

[figure not shown]
[figure not shown]
[figure not shown]

Figure 2. Representation of a linear and a radial hyperplane in a Support Vector Machine classifier.

Class 1: squares, class 2: circles, and in blue the boundary cases.

Figure 3. Representation of a Random Forest classifier, with n trees

The circles represent the nodes, with the red and green circles signalling the terminal nodes, and the arrows show the “optimal split” computed for each node of each tree. The aggregated vote of all (n) trees is then combined and expressed as a final classification, for example, “alive”.

Table 1. Specific research questions with add-on measurements

Short title	Research questions	Primary outcome
Basic study	Which combination of clinical variables obtainable through physical examination is associated with cardiac output measured by critical care ultrasonography (CCUS)? Which combination of clinical and haemodynamic variables is associated with 7-day, 30-day and 90-day mortality?	Cardiac output Mortality

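### Choosing the cardiac index cut-off with the highest AUC cannot show where signs of hypoperfusion appear, because AUC depends on where a cut-off lies in the distribution even when there is no threshold

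*SAP*

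**What the plan says.** SAP section 6.5.1 names two candidates at each end: "Cut-offs for a low cardiac index: 2.2 and 2.5 L/min/m²" and "Cut-offs for a high cardiac index: 4.0 and 4.5 L/min/m²". Logistic models are fitted to the dichotomised cardiac index, and the choice between candidates is then stated: "We will identify the cardiac index cut-off(s) where clinical examination has the best discriminative value", with the area under the ROC curve as the criterion.

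Section 6.5.2 makes the layout of the accuracy tables follow from that choice: "Depending on the optimal and number of cut-offs". A note under its 2 × 2 table allows any of the four values, and 98.5% intervals are planned.

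Section 7 (Discussion) gives the purpose. The second diagnostic step is to find the level of cardiac index at which signs of hypoperfusion start to show. It continues: "We aim to present a cut-off for low cardiac index relevant to critically ill patients in our secondary outcome", and "Diagnostic test accuracies will be described for each finding or combinations of findings for our proposed cut-off of cardiac index". It also says that this secondary analysis "will be considered exploratory and we will emphasise the need for validation in an independent cohort".

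**The concern.** The plan uses AUC to answer a question about location: at what cardiac index do the signs appear? AUC measures how well a score separates the patients on either side of a cut-off. That separation grows as the cut-off moves away from the centre of the distribution, whether or not anything changes at that point. A best-AUC rule therefore returns a winner even when the relation is a plain straight line.

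At stake is a published cut-off for low cardiac index in critically ill patients, presented as clinically meaningful, that may reflect only the spread of this cohort or sampling noise. The SAP contains no test for a threshold or for non-linearity against continuous cardiac index that would expose this.

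**Working it through.** **Inputs from the SAP.** n = 1075 and SD of cardiac index 0.99 (section 3.2.1); cut-offs 2.2, 2.5, 4.0 and 4.5 (section 6.5.1).

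**Assumptions.** The SAP gives no mean cardiac index, so it is varied from 2.4 to 3.35. The correlation between sign score and cardiac index is set at r = 0.3, the lower end of what section 6.2.1 calls medium. The single-sign pilot slopes in section 3.2.1 imply less: 0.040 × 0.98 / 0.99 = 0.04 for urine output and 0.045 × 2.4 / 0.99 = 0.11 in absolute size for capillary refill time. A combined score could be stronger.

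**The plan's nearest figure.** The SAP gives no number for the cut-off choice. The closest figure using the same n and SD is the power of 0.81 for a slope of 0.10 on urine output. With residual SD √(0.99² − 0.098²) = 0.985, a two-sided slope test at 0.015 gives 0.795. That is near enough to confirm the reading of n and SD, and this power is not in dispute here.

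**AUC with no threshold.** Let cardiac index be μ + 0.99·(r·S + √(1 − r²)·ε), with S and ε independent standard normal, so that the relation is strictly linear. For cut-off c put z = (c − μ)/0.99 and p(s) = Φ((r·s − z)/√(1 − r²)). The score density is φ(s)·p(s)/Φ(−z) above the cut-off and φ(s)·(1 − p(s))/Φ(z) below it. AUC is the integral of the first density times the distribution function of the second. It depends only on r and the distance |z| from the mean.

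At r = 0.3:

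| Assumed mean | 2.2 | 2.5 | 4.0 | 4.5 |
|---|---|---|---|---|
| 2.5 | 0.638 | 0.636 | 0.675 | 0.702 |
| 2.75 | 0.642 | 0.637 | 0.664 | 0.688 |
| 3.0 | 0.648 | 0.641 | 0.654 | 0.675 |
| 3.35 | 0.660 | 0.649 | 0.644 | 0.660 |

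With the mean at 2.75, moving the cut-off along the whole scale shows the mechanism: AUC is 0.688 at 1.0, 0.646 at 2.0, 0.636 at 2.75 (the mean), 0.646 at 3.5 and 0.688 at 4.5. Nothing changes at any of these points except distance from the mean.

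**Gaps between paired cut-offs.** High pair: 0.702 − 0.675 = 0.027 at mean 2.5, falling to 0.660 − 0.644 = 0.016 at mean 3.35. Low pair: 0.638 − 0.636 = 0.002 at mean 2.5, rising to about 0.010 at mean 3.35 (0.011 from the rounded entries). At mean 2.4 the low gap is about 0.001. The sampling SD of AUC at the low cut-offs is 0.017–0.025, larger than the gap itself.

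**The rule applied to samples of 1075**, fixed score, means 2.4 to 3.35:
- 4.5 beats 4.0 in about 71–79%.
- 2.2 beats 2.5 in about 51–73%.
- Mean excess of the AUC at the chosen cut-off over its true value: about 0.004–0.006 (low pair) and 0.006–0.015 (high pair).

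**Sensitivity to r.** At r = 0.1 and mean 2.75 the AUCs are 0.547 / 0.546 / 0.555 / 0.564; at r = 0.5 they are 0.738 / 0.732 / 0.770 / 0.804. The ordering is the same and only its size changes.

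**The case against.** The strongest reply is that the SAP already contains this analysis. Only four pre-specified values compete, and both low ones have precedents cited in section 6.1.2. That section says both cut-offs at each end will be used, and section 6.5.2 permits tables at all four. The primary analysis keeps cardiac index continuous. Section 6.2.4 plans a bootstrap for both studies. Section 7 calls the work exploratory and asks for external validation.

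Most of this is true and limits the consequence: no primary result is touched. It does not rescue the rule. Section 6.5.2 permits all four values without committing to them, and section 7 ties accuracy to the proposed cut-off. The bootstrap is described for building the model and selecting variables; nothing says the cut-off choice is repeated in it. Validation deals with optimism, not with a rule aimed at the wrong quantity: a second cohort with a similar distribution would tend to favour the same cut-off.

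Three stronger readings are tempting and should not be drawn:
- **Accuracy is materially overstated by the choice.** The choice alone adds little. A simulation with ten-predictor models at R² 0.09 gave apparent AUC 0.69–0.76 against 0.64–0.66 in new data, but that gap includes ordinary overfitting, which is a separate matter.
- **Distributional position dictates the low cut-off.** It pulls clearly on the high pair. For the low pair, the one section 7 singles out, noise largely decides.
- **A skewed outcome reverses 2.2 and 2.5.** With a gamma-shaped outcome this happened at assumed means 2.5 and 2.7 but not at 3.0. The SAP gives neither mean nor shape, so no direction can be claimed.

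**Conclusion.** The point holds as one of interpretation. A best-AUC rule returns a preferred cut-off under a relation with no threshold, so it cannot identify a clinically meaningful one. The high-pair choice leans toward the value further from the mean, and the low-pair choice is close to arbitrary. The percentages rest on a normal, linear model with r = 0.3 and a mean the SAP does not state; the qualitative result under that model, AUC lowest at the mean and rising with distance, held at every r examined from 0.1 to 0.5. The reach is confined to one exploratory secondary analysis and the threshold it would propose.

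**What to change.** - In section 6.5.1, delete the selection by highest AUC. In section 7, delete the statement that the analysis will yield a proposed low cut-off.
- In section 6.5.2, commit to AUC and all accuracy measures, with the 98.5% intervals already planned, at each of 2.2, 2.5, 4.0 and 4.5, whichever AUC is highest.
- Extend the section 6.2.4 bootstrap to give an optimism-corrected AUC at each cut-off.
- For the question of where signs appear, model the probability of each sign against continuous cardiac index with a spline, show the curve, and test for non-linearity before any threshold is claimed.

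The cost is a few more table columns and one spline model per sign. No new data are needed.

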6.5.2. Diagnostic test evaluation

Depending on the optimal and number of cut-offs (i.e. low or normal cardiac index or low, normal and high cardiac index), we will display our diagnostic test in a 2 x 2 table, 2 x 3, or a 3 x 3 table (28,29). An example table can be found below. In a 3 x 3 table, data will be ordinal and we will give an indication of the agreement with the weighted kappa (30).

		Cardiac index cut-offs		
		Low (< 2.5)	Normal (2.5 to 4.5)	High (> 4.5)
EXAMPLE: Capillary refill time	Prolonged	True positive (a)	False positive (d)	False positive (d)
	Normal	False normal (b)	True normal (d)	False normal (b)
	Shortened	False negative (c)	False negative (c)	True negative (d)

Subsequently, we will calculate sensitivity, specificity, positive and negative predictive values and positive and negative likelihood ratios. Because this can only be calculated in 2 x 2 tables, we will cut the 3 x 3 table in low/normal and normal/high cut-offs:

		Cardiac index below/above x L/min/m ²	
		Yes	No
Clinical examination finding(s) present	Yes	True positive (a)	False positive (c)
	No	False negative (b)	True negative (d)

Explanation: x can be 2.2, 2.5, 4.0 or 4.5 L/min/m².

In addition, we will also calculate the 98.5% confidence intervals. Below we interpret each diagnostic test parameter for our diagnostic study.

- True positive: the number of patients with a low cardiac index who also had clinical examination signs indicating *hypoperfusion*.
- False positive: the number of patients without a low cardiac index, but with clinical examination signs indicating *hypoperfusion*.
- True negative: the number of patients without a low cardiac index and with clinical examination signs indicating *a normal* perfusion.
- False negative: the number of patients with a low cardiac index, but with clinical examination signs indicating *a normal* perfusion.
- Sensitivity: the probability of the presence of a low cardiac index when there were clinical examination signs indicating *hypoperfusion*.
- Specificity: the probability of the absence of a low cardiac index when clinical examination signs indicating *a normal* perfusion.
- Positive predictive value: the probability that a low cardiac index is present given the clinical examination signs indicate *hypoperfusion*.
- Negative predictive value: the probability that a low cardiac index is absent given the clinical examination signs indicate *a normal* perfusion.

6.6. Additional analyses: machine learning

6.6.1. *Model development: algorithms, training and testing*

We will use machine learning (ML) algorithms to generate hypotheses, validate observations of conventional models, and to unravel heterogeneity. Predictive modelling using ML algorithms requires the original data be split into two smaller sets, one for training and one for testing. We randomly split the original data into two groups with, respectively, 70 to 80% and 20 to 30% of the individuals. The split before further division of the training data into several folds for cross-validation virtually assures no information leakage is possible, making the training method virtually completely unbiased.

The training set will then be further divided into k similarly sized partitions (k -folds). By doing this, we divide the training set each time into k parts and then use each of these k parts once as testing dataset for the model trained on the other $k-1$. During this process, the hyper-parameters defining the model are optimized, with the performance measures (AUROC, accuracy, or a measurement of error, depending on whether the analysis is regression or classification) being presented as the average of those k runs of the algorithm. Additionally, this process can be repeated r number of times, where the average of r error terms obtained after performing k -fold cross validation r times is calculated.

This will be done for each of the algorithms, so as to determine the optimal values of all modifiable hyper-parameters of each model and maximize the models' performance metrics (usually the Area Under the Receiver Operating Characteristic curve (AUROC) for classification). When deemed

necessary, an additional post-hoc sensitivity analysis will be done to refine the parameters beyond what the tuning functions in R allow.

Three algorithms will primarily be used to develop the models: Gradient Boosted Machine, Support Vector Machine, and Random Forest. A summary of the necessary hyper-parameters for each of the algorithms is provided in table 3. Finally, an Ensemble Model will be built consisting of the best models build with each of the three algorithms. The choice for these three models is based on them having previously been shown to have similar, high performances in datasets with sparse data, despite the different structure of each algorithm (31). All three algorithms are not very sensitive to over-fitting (i.e. tend not to over-fit), but achieve this in different ways, where SVM is a disadvantage compared to the other two, since it attempts to minimize over-fitting for each kernel (i.e. type of model), but the user is still left to determine which kernel best fits the data, which can be error prone (32). In addition, both GBM and Random Forest are tree-based algorithms which allow for almost unprocessed data to be analysed. While SVM requires significant pre-processing, and is computationally slower than the other two, its high performance and the possibility to adapt a Radial Basis Function to almost all high-dimensionality problems makes it an easy-to-use, rather interpretable algorithm.

6.6.2. *Gradient Boosting Machine*

The Gradient Boosting Machine (GBM) algorithm is perhaps the strongest and the one with potentially the most interesting clinically-oriented properties. In GBM, new models are consecutively fitted to the training data set in order to provide a more accurate estimate of the outcome variable (33). By combining multiple decision trees, and increasingly weighting the “difficult to predict” events to a greater degree, GBM will fit k models (one per fold of the cross-validation process we defined earlier) to compute the error estimate, before making a final model using all of the data.

Our GBM model was tuned during training for four hyper-parameters: n.trees (the number of iterations to be generated by the algorithm), n.minobsinnode (the minimum number of observations in the terminal nodes of a tree (see Fig. 5)), interaction depth (defines the number of terminal nodes or leaves of a tree), and shrinkage (34). This parameter controls the learning rate of the algorithm by controlling the rate at which the boosting algorithm descends the error surface (35,36) .

6.6.3. *Support Vector Machine*

A Support Vector Machine (SVM) is a class of supervised learning algorithms often used in classification problems such as this. It classifies data points into two different classes (e.g. “Alive” or “Deceased”) by taking these points in a multidimensional space and separating them by means of the hyperplane that best differentiates between the two groups (37). Due to the great variation in range of our numeric

predictor variables in datasets with patient data, the data will be scaled and centred, to prevent attributes with a greater range dominating those with smaller ranges. Since SVMs don't allow for categorical variables, further processing is needed to encode all categorical variables into dummy variables (binary variables (0 or 1) which indicate the absence or presence of the effect of some parameter). After this, variables with zero or near-zero variance are excluded.

The SVM model will be tuned during training for two hyper-parameters: sigma (σ) and cost (C) (34). The best values for various pairs of exponentially growing C and sigma values will be determined during training by means of a "grid-search" using cross-validation (37,38). In addition, due to the expected dimensionality of the classification problem, we will use a Radial Basis Function (RBF) kernel to allow the hyperplane boundary between classes to be non-linear. Tuning of sigma is required in this context to determine the influence of a single training example on the overall prediction. For instance, an excessively large value would constrain the model back to linearity (37). Similarly, cost will control the misclassification tolerance by forcing the SVM towards a harder margin or allowing a smoother (i.e. softer) decision boundary and an increased probability of misclassification.

6.6.4. *Random Forest (figure 3)*

A Random Forest (RF) is an ensemble-based technique that attempts to minimise the limitations of classical decision trees by building multiple trees from a random subset of the original training data and considering only a random number of predictor variables at each split, instead of trying all the variables at every split, before aggregating their results (39-41).

As a learning method, it is more robust to overfitting than normal decision trees, which is especially important in relatively small training sets, and shows good predictive performance despite considerable noise (37). Furthermore, it requires virtually no pre-processing, running efficiently even on datasets with a large number of input variables, categorical and continuous.

Hyper-parameter optimization is done by defining a parameter-value grid with a wide range of trees and multiple values for *mtry*. The best model is selected either by comparison of the AUROCs obtained for each combination of these two parameters, or according to Kuhn and Johnson's threshold-based approach for datasets with imbalanced outcome classes (42).

6.6.5. *Ensemble models*

Lastly, an ensemble model will be built that combined the best model of each of the three base learner algorithms. Using an ensemble model is expected to increase model robustness, when compared to using individual models, which is achieved by incorporating the predictions from all the base learners.

The final predictions are then given twice, one label per type of ensemble: for the weighted ensemble, based on the weights defined for each model, the weighted predicted probabilities are calculated, and a label (e.g. “Alive” or “Deceased”) is given to a case based on the defined threshold (of 0.50 in this case); for the majority vote ensemble, the label, and not the predicted probabilities, of each model are taken, and the class with at least two-out-of-three votes is attributed to a certain patient.

6.6.6. *Model testing*

All final models (for each algorithm or for the ensemble model) will be fitted to the testing dataset, resulting in a prediction of each patient’s individual probabilities of belonging to either of the outcome classes (“Alive” or “Deceased”). Based on a defined threshold, these probabilities will then be converted to a binary label, and the AUROC and other additional performance measures for the models will be calculated for the testing dataset.

6.6.7. *Principal Component Analysis*

The robust implementation of all three algorithms used to model ICU mortality prediction in the SICS-I database in the caret package used in R, allows us to obtain an importance-based ranking of the variables, with respect to their ability to predict the outcome variable. This feature is potentially applicable in clinical practice and provides an intuitive way to reduce the dimensionality (i.e. number of input variables). However, Principal Component Analysis (PCA) can be an even better tool to shed light on parameter prioritization for data-driven studies in the ICU.

PCA is an adaptive data analysis technique for reducing the dimensionality of large datasets, thus increasing interpretability, while simultaneously minimizing information loss. It identifies the largest sources of variation in a dataset and constructs a lower dimensional subspace of the data by creating new uncorrelated variables, or principal components (PCs), that successively maximize variance (43). To form each additional PC, it seeks a second linear combination that can explain the maximum of the remaining variance. For each PC, variable loadings are then provided, which represent the contribution of each original variable in explaining the variance in each of the PCs. Unlike predictive modelling, PCA is a descriptive tool, rather than inferential or predictive, which can partly substantiate or explain the predicted findings.

With iterative PCA, a variation on normal PCA, scores for both variables and individuals of complete or incomplete datasets are returned, providing an idea of the contribution of a certain variable, or a certain individual, to the total variance in that dataset (44). PPCA and BPCA are both iterative techniques with a probabilistic basis, which have been shown to perform better than traditional PCA when applied to data with missing values, especially as the missingness level increases (43). Using the

The R packages *factoextra* (45) and *factoMineR* (46), the PCA results are presented graphically by means of a graphic showing the distribution of individuals across a plane containing two PCs, a correlation circle graphic with the most explanatory variables or factors for each PC, and the PCA biplot showing a combination of both for clarity. The squared cosine (\cos^2) of the most relevant individuals and variables is also given, as is their percentual contribution (47).

Due to the heterogeneity in variable scaling (for example, the maximal urine per hour was 600 ml/hour, the highest value for haematocrit being 0.53, and 11.5 mmol/L for haemoglobin), all variables were centred and scaled (i.e. subtracting the variable mean, and dividing the value by the standard deviation), so as to standardise the variance of the dataset, allowing for comparability between variables with different scales and units (48).

